8.8 Investigational Device Malfunction

Any occurrences of malfunction of the Holder or Charger will be documented by the Investigator or his/her designated staff using a Device Issue Log.

Confidentiality statement: Data and information contained in this document are considered to constitute trade secrets and confidential commercial information, and the legal protections provided to such trade secrets and confidential information are hereby claimed under the applicable provisions of applicable law. No part of this document may be publicly disclosed without the written consent of Philip Morris Products S.A.

Furthermore, any malfunctions of the Holder or Charger that lead to an AE/SAE will follow the same processes as described above.

9 STUDY ACTIVITIES

A detailed schedule of assessment can be found in Appendix 1. The time points shown are to be considered the time of assessment for the first subject. As not all subjects can be treated at the same time, a short time window will be implemented for subsequent subjects. Measurements not conducted at the exact time point, but conducted within the given time window (if applicable), do not constitute a protocol deviation but an accepted variability for the given time point.

In general, if no start time for the procedures is provided, then the procedure can be performed at any time during the day.

9.1 Screening Visit

The Screening Visit will be performed within 4 weeks (Day -30 to Day -3) prior to admission (Day -2). Subjects will attend the investigational site in at least 8-hour fasting state for clinical laboratory parameters to be assessed. Table 6 shows the assessments that will be performed at the Screening Visit. First, the ICF/subject information sheet should be given to the subject. When/if the ICF/subject information sheet is signed, the other screening procedures can be performed in the order deemed most practical. While it is recommended to complete as much screening procedures as possible in one day, it is permissible to complete those over more than one day. Smoking is allowed during screening.

Table 6. Time Schedule - Screening Visit

| Time (Day-30 to Day-3) | Blood sample | Procedures | Additional information |
|------------------------------|-----------------|---|------------------------|
| Start of procedure | | Screening | |
| | | Informed consent/Subject Information Sheet and Informed consents/subject information sheets for the two bio-banking | |
| | | Advice on the risk of smoking and debriefing | |
| | | Demographic data collected | |
| | | Identification of current CC brand | |
| | | Medical history/concomitant disease | |
| | | Prior medication (4 weeks prior to Screening Visit) and concomitant medication | |
| | | Smoking history | |

Confidentiality statement: Data and information contained in this document are considered to constitute trade secrets and confidential commercial information, and the legal protections provided to such trade secrets and confidential information are hereby claimed under the applicable provisions of applicable law. No part of this document may be publicly disclosed without the written consent of Philip Morris Products S.A.

| Time (Day-30 to Day-3) | Blood sample | Procedures | Additional information |
|-------------------------------|-----------------|--|---|
| Start of procedure | | Screening | |
| | | Willingness to quit smoking within the next 3 months and to abstain from smoking for at least 5 days | |
| | | Vital signs (blood pressure, pulse rate, respiratory rate) | At least 5 minutes in supine position prior to measurement |
| | √ | Clinical laboratory parameters (hematology, urine analysis, clinical chemistry) | To be done after at least 8 hours of fasting |
| | √ | HIV, hepatitis B and C | |
| | | Physical examination and height, weight, calculation of BMI | |
| | | THS 2.2 product demonstration | |
| | | Chest X-ray (if not performed within 6 months prior to Screening Visit) | |
| | | Urine drug screen | |
| | | Urine cotinine screening test | |
| | | Alcohol breath test screen | |
| | | Urine pregnancy test (all females) | |
| | | FTND | |
| | | Spirometry without short-acting bronchodilator first, and then with | To be done at least 1 hour after smoking |
| | | ECG | At least 10 minutes in supine position prior to recording |
| | | AE/SAE recording | If the Screening Visit is performed on two separate days the AE/SAE questions will be asked again |
| | | Inclusion/exclusion criteria | |

Abbreviations: AE = adverse event; BMI = body mass index; CC = conventional cigarette(s); ECG = electrocardiogram; FTND = Fagerström Test for Nicotine Dependence; HIV = human immunodeficiency virus; SAE = serious adverse event; THS 2.2 = Tobacco Heating System 2.2.

9.2.1 Admission (Day -2)

The procedures of Day -2 can be performed in order deemed most practical except product test which will be the last assessment prior to enrolment after all eligibility criteria have been met. Table 7 shows the assessments that will be performed at Admission (Day -2):

Table 7. Time Schedule - Day -2

| Time | Blood sample | Procedures | Additional information |
|-------------------------------|--------------|--|--|
| Start of procedure | | Admission | |
| | | AE/SAE recording; concomitant medication, Urine pregnancy test (all females only) Advice on the risk of smoking and debriefing Smoking history Willingness to abstain from smoking for at least 5 days Urine drug screen Urine cotinine screening test Alcohol breath test screen CO breath test | All day |
| | | Vital signs (blood pressure, pulse rate, respiratory rate) Physical examination, weight, BMI Inclusion/exclusion criteria Identification of current CC brand and picture THS 2.2 product test | At least 5 minutes in supine position prior to measurement |
| Until 11:00 PM | | Smoking Period | |
| In the evening until 09:00 PM | | Dinner | |
| | | Enrolment | Only after all eligibility criteria have been met |
| 11:00 PM | | End of study day | |

Abbreviations: AE = adverse event; BMI = body mass index; CC = conventional cigarette(s); CO = carbon monoxide; SAE: serious adverse event; THS 2.2= Tobacco Heating System 2.2.

Confidentiality statement: Data and information contained in this document are considered to constitute trade secrets and confidential commercial information, and the legal protections provided to such trade secrets and confidential information are hereby claimed under the applicable provisions of applicable law. No part of this document may be publicly disclosed without the written consent of Philip Morris Products S.A.

9.2.2 Baseline Period (Day -1 to Day 0)

Table 8 and Table 9 show the assessments that will be performed at baseline (Day -1 and Day 0, respectively).

The start times given are for the first subject. All subsequent subjects should complete procedures within the time window given in the tables.

Table 8. Time Schedule - Day -1

| Time | Blood sample | Procedures | Additional information |
|-------------------------------|--------------|--|--|
| Start of procedure | | Baseline Day -1 | |
| | | AE/SAE recording; concomitant medication | All day |
| 06:30 AM+/- 30min | | Start urine collection to Day -1 sampling bottle | |
| | | CO breath test | To be done within 15 minutes prior to smoking |
| 06:30 AM | | Beginning of smoking period | |
| Before 10:00 AM | | Breakfast | |
| before 12:00 PM | | Vital signs (blood pressure, pulse rate, respiratory rate) | At least 5 minutes in supine position prior to measurement |
| 12:00 PM- 02:00 PM | | CO breath test | |
| before 03:00 PM | | Lunch | |
| 04:00 PM- 06:00 PM | | CO breath test | |
| Afternoon | | Snacks | |
| In the evening until 09:00 PM | | Dinner | |
| 08:00 PM- 10:00 PM | | CO breath test | |
| 08:00 PM- 10:00 PM | √ | COHb in blood | |
| 08:00 PM- 11:00 PM | | MCEQ questionnaire , QSU-brief questionnaire | |
| 11:00 PM | | End of smoking period | |

Confidentiality statement: Data and information contained in this document are considered to constitute trade secrets and confidential commercial information, and the legal protections provided to such trade secrets and confidential information are hereby claimed under the applicable provisions of applicable law. No part of this document may be publicly disclosed without the written consent of Philip Morris Products S.A.

06:30 AM-
11:15 PM

Collection of all smoked CC butts

For accountability

Abbreviations: AE = adverse event; CC = conventional cigarette(s); CO = carbon monoxide; COHb = carboxyhemoglobin; MCEQ = Modified Cigarette Evaluation Questionnaire; QSU-brief = Questionnaire of Smoking Urges (brief version); SAE= serious adverse event; THS 2.2 = Tobacco Heating System 2.2.

**Table 9. Time Schedule - Day 0**

| Time | Blood sample | Procedures | Additional information |
|---------------------------|--------------|--|---|
| Start of procedure | | Baseline Day 0 | |
| | | AE/SAE recording; concomitant medication | All day |
| | | Randomization | At any time during the day after eligibility criteria have been met. Subjects are not to be informed of their assigned arm until Day 1. |
| 06:29 AM +/-30 min | | Analysis sample to be taken after final portion of urine has been added to Day -1 sampling bottle. | BoExp and creatinine in 24-hour urine |
| 06:30 AM +/-30 min | | Start of urine collection to Day 0 sampling bottle | |
| | | Assessment of cough (VAS) | To be done prior to smoking but no later than 10:00 PM |
| | | MNWS questionnaire | To be done prior to smoking but no later than 10:00 PM |
| | | Spirometry without short-acting bronchodilator | To be done prior to smoking |
| | √ | CYP2A6 activity in plasma | To be done prior to smoking |
| | | CO breath test | To be done within 15 minutes prior to smoking |
| | | HST | HST SODIM [®] device has to be used for all product uses if compatible CCs are smoked |
| 06:30 AM | | Beginning of smoking period | |
| | √ | Clinical laboratory parameters (hematology, clinical chemistry) | To be done after at least 8 hours of fasting |
| | √ | Bio-banking for BoExp/ risk markers in serum/plasma (if consent is obtained) | To be done after at least 8 hours of fasting |
| | √ | Bio-banking for transcriptomics (if consent is obtained) | To be done after at least 8 hours of fasting |
| | | Urine safety analysis | |
| Before 10:00 AM | | Breakfast | |

Confidentiality statement: Data and information contained in this document are considered to constitute trade secrets and confidential commercial information, and the legal protections provided to such trade secrets and confidential information are hereby claimed under the applicable provisions of applicable law. No part of this document may be publicly disclosed without the written consent of Philip Morris Products S.A.

| Time | Blood sample | Procedures | Additional information |
|-------------------------------|--------------|---|--|
| Start of procedure | | Baseline Day 0 | |
| 10:00 AM-12:00 PM | | Vital signs (blood pressure, pulse rate, respiratory rate) | At least 5 minutes in supine position prior to measurement |
| 10:00 AM-12:00 PM | | A cup of coffee containing approximately 150 mg of CAF | |
| 12:00 PM-02:00 PM | | CO breath test | |
| before 3:00 PM | | Lunch | |
| 04:00 PM-06:00 PM | √ | CYP1A2 activity in plasma | 6 hours +/-15 minutes after intake of cup of coffee |
| 04:00 PM-06:00 PM | | CO breath test | |
| afternoon | | Snacks | |
| In the evening until 09:00 PM | | Dinner | |
| 08:00 PM-10:00 PM | | CO breath test | |
| 08:00 PM-10:00 PM | √ | COHb in blood | |
| 08:00 PM-10:00 PM | √ | Nicotine, cotinine in plasma | |
| 08:00 PM-11:00 PM | | HST questionnaire | |
| 08:00 PM- 11:00 PM | | MCEQ questionnaire (THS 2.2 and CC arms only), QSU-brief questionnaire | |
| 11:00 PM | | End of smoking period | |

Confidentiality statement: Data and information contained in this document are considered to constitute trade secrets and confidential commercial information, and the legal protections provided to such trade secrets and confidential information are hereby claimed under the applicable provisions of applicable law. No part of this document may be publicly disclosed without the written consent of Philip Morris Products S.A.

| Time | Blood sample | Procedures | Additional information |
|---------------------------|--------------|----------------------------|------------------------|
| Start of procedure | | Baseline Day 0 | |
| 6:30 AM-11:15 PM | | Collection of all CC butts | For accountability |

Abbreviations: AE = adverse event; BoExp = biomarkers of exposure; CAF = caffeine; CC = conventional cigarette(s); CO = carbon monoxide; COHb = carboxyhemoglobin; CYP1A2 = Cytochrome P450 1A2; CYP2A6 = Cytochrome P450 2A6; HST = human smoking topography; MCEQ = Modified Cigarette Evaluation Questionnaire; MNWS = Minnesota Nicotine Withdrawal Scale (revised version); QSU-brief = Questionnaire of Smoking Urges (brief version); SAE = serious adverse event; THS 2.2 = Tobacco Heating System 2.2; VAS = Visual analogue scale.

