Charger The function of the Charger (Model 4) is to recharge the Holder after use. It contains a battery with sufficient capacity to recharge the Holder approximately 20 times. It is a convenient size to carry around, and can itself be recharged from a mains power source.

Confidentiality statement: Data and information contained in this document are considered to constitute trade secrets and confidential commercial information, and the legal protections provided to such trade secrets and confidential information are hereby claimed under the applicable provisions of applicable law. No part of this document may be publicly disclosed without the written consent of Philip Morris Products S.A.

| | |
|---------------------------------|---|
| CC | The term ‘conventional cigarette’ refers to manufactured and commercially available cigarettes and excludes hand-rolled cigarettes, cigars, pipes, bidis, and other nicotine-containing products. |
| CC incompatible with HST device | All CCs that are incompatible with the HST device (e.g. slim CC). |
| Day of Discharge | Day 6 |
| End of the study | End of Study is defined as the time of discharge on Day 6 plus 7-day follow-up period. |
| Enrolment | On Day -2 for eligible subjects after all applicable inclusion and exclusion criteria have been satisfactorily met and the subject is willing and ready to use THS 2.2 (the test of THS 2.2 is the last assessment prior to enrolment). |
| Exposure period | 06:30 AM of Day 1 until 11:00 PM of Day 5. |
| Randomization | Assignment of the subject randomization number in the Interactive Web and Voice Response System. This can be done any time on Day 0, however, subjects are not to be informed of their randomization group and number prior Day 1. |
| Run-in period | Admission to site until 06:29 AM of Day -1. |
| Safety follow-up | After the time of Discharge, a 7-day safety follow-up will be done for the recording of spontaneously reported new adverse events (AEs)/serious adverse events (SAEs) and the active follow-up of ongoing AEs/SAEs. In general, any AE will be actively followed-up until resolved, stabilized, (i.e., no worsening of the event), or a plausible explanation for the event has been found. |
| Screening failure | Subjects who do not meet the entry criteria from informed consent form (ICF/subject information sheet) signature to the time of enrolment will be considered a screening failure and will be replaced by other subjects. |

| | |

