6.3 Method for Assigning Subjects to Study Arms

When all the eligibility criteria have been met, randomization will be done through the Interactive Web and Voice Response System on Day 0 at any time during the day. Subjects will be informed of their randomized study arm in the morning of Day 1, prior to 06:30 AM.

Subjects will be randomized to one of the 3 study arms: THS 2.2:CC:SA in a 2:1:1 ratio. Stratified randomization will be conducted by sex and by average daily CC consumption in the 4 weeks prior to the Screening Visit as reported by the subject (those smoking 10 to 19 CC and those smoking >19 CC per day). In each arm, each sex and each of the smoking strata should have a quota applied to ensure they represent at least 40% of the population.

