7.8.4.3 Modified Cigarette Evaluation Questionnaire

Product evaluation will be assessed using the MCEQ (Cappelleri et al, 2007). The MCEQ assesses the degree to which subjects experience the reinforcing effects of smoking, by measuring:

- Smoking satisfaction (satisfying, tastes good, enjoys smoking).
- Psychological rewards (calms down, more awake, less irritable, helps concentrate, reduces hunger).
- Aversion (dizziness, nauseous).
- Enjoyment of respiratory tract sensations (single-item assessment).
- Craving reduction (single-item assessment).

Confidentiality statement: Data and information contained in this document are considered to constitute trade secrets and confidential commercial information, and the legal protections provided to such trade secrets and confidential information are hereby claimed under the applicable provisions of applicable law. No part of this document may be publicly disclosed without the written consent of Philip Morris Products S.A.

Only subjects who are randomized to the THS 2.2 and CC arms will complete this questionnaire. The subjects will complete the questionnaire by themselves.

The MCEQ will be completed by subjects during the confinement period from Day -1 to Day 5.

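### The Day 0 evening MCEQ is limited to the THS 2.2 and CC arms, so a subject allocated to smoking abstinence could infer the arm before the planned disclosure on Day 1

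*Protocol*

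**What the plan says.** Protocol Section 6.3 places randomization "on Day 0 at any time during the day". Disclosure is a separate, later step: "Subjects will be informed of their randomized study arm in the morning of Day 1, prior to 06:30 AM". The randomization row of Table 9 repeats this ("Subjects are not to be informed of their assigned arm until Day 1"), as does the definition of randomization in the Protocol's Explanation of Terms ("subjects are not to be informed of their randomization group and number prior Day 1"). SAP Section 6.1 gives the same time of disclosure.

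The MCEQ is scheduled from 08:00 to 11:00 PM on both baseline evenings. Table 8 (Day -1) lists it without an arm label: "MCEQ questionnaire , QSU-brief questionnaire". Table 9 (Day 0) lists it as "MCEQ questionnaire (THS 2.2 and CC arms only), QSU-brief questionnaire".

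Protocol Section 7.8.4.3 states the restriction generally: "Only subjects who are randomized to the THS 2.2 and CC arms will complete this questionnaire". It then sets the days: "The MCEQ will be completed by subjects during the confinement period from Day -1 to Day 5". SAP Section 7.3.3 has the same days, hours and arms, and SAP Section 12.6.3.1.2 says that the SA arm has no MCEQ data. Table A1 in both documents carries the arm label next to dots on both baseline days.

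**The concern.** The Protocol chose to keep the allocation from subjects until baseline is over. A form that everyone completes on one evening, and that only two of the three arms complete on the next, works against that choice. Subjects are confined together, so an omission may be noticed.

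Baseline is the issue. In general it is the last value before about 06:30 AM on Day 1 (Protocol Section 12.1.2, SAP Section 12.1.4), so the Day 0 evening supplies values that enter the models as covariates. Smoking is allowed until 11:00 PM. A subject who works out that abstinence starts next morning could smoke differently in the remaining hours, or rate smoking urges differently. The SA baseline would then depend in part on the allocation, which a baseline covariate should not.

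**Working it through.** The plan gives no figure to reproduce. The check sets the passages side by side, with simple arithmetic on the allocation ratio and the clock.

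**1. Order of events on Day 0.** Randomization may fall anywhere in the day, so there are two cases.
- Randomization before the MCEQ: the restriction can be applied, and applying it sorts subjects by arm before disclosure.
- Randomization after the MCEQ: no arm exists yet, so the restriction cannot be applied. Nothing leaks, but Table 9 cannot be followed as written.

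**2. What the form reveals in the first case.** The 2:1:1 ratio gives prior probabilities of 50% (THS 2.2), 25% (CC) and 25% (SA). If the form goes to THS 2.2 and CC only:
- Not given the form: P(SA) = 0.25 / 0.25 = 100%.
- Given the form: P(THS 2.2) = 0.50 / 0.75 = 66.7%; P(CC) = 0.25 / 0.75 = 33.3%; P(SA) = 0.

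An SA subject who recognises the omission can identify the arm; that is 40 / 160 = 25% of subjects. A recipient can rule out SA, but the odds of THS 2.2 to CC stay at 2:1.

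**3. How early the cue comes.** From 08:00-11:00 PM on Day 0 to 06:30 AM on Day 1 is 10.5 down to 7.5 hours. Permitted smoking left that evening is 3 down to 0 hours. The daily smoking window, 06:30 AM to 11:00 PM, is 16.5 hours, so at most 3 / 16.5 = 18% of it follows the cue. This bounds the smoking time affected; it is not an effect size.

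**4. Which baseline values overlap.**
- QSU-brief: same row and window of Table 9 as the MCEQ. Its baseline is a covariate in the repeated-measures model, which reports THS 2.2 - SA as well as THS 2.2 - CC (SAP 12.6.3.1.1).
- COHb: 08:00-10:00 PM in Table 9; the baseline covariate for one primary endpoint (SAP 12.6.1.1), also compared with SA as a secondary analysis (SAP 12.6.2.1).
- Exhaled CO: baselines are time-matched to Day 0 (SAP 12.6.2.1), so only the fourth test, at 08:00-10:00 PM, overlaps.
- 24-hour urine: the Day 0 collection ends at 06:29 AM on Day 1, so the cue falls in its last part.

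**5. Whether another passage resolves it.** None does for the MCEQ. Footnote m of Table A1 does so for human smoking topography (HST): the row is labelled for the THS 2.2 and CC arms, but the footnote gives Day 0 HST to all subjects with compatible cigarettes and applies the arm restriction to Days 1 and 4. Footnote l, on the MCEQ, gives only the days.

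**The case against.** The best counter-argument is that the label in Table 9 is a drafting carry-over. The same words appear in the tables for Days 1 to 5. Section 7.8.4.3 applies the restriction from Day -1 as well, before any arm exists, so it cannot be literal there. This is plausible but not shown: Table 8 omits the label, Table 9 includes it, and no footnote makes an exception. Either way the text needs reconciling.

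Several limits stand. Disclosure is by inference: an SA subject must notice the omission and interpret it, and no passage says that subjects are told which arms complete the MCEQ. The order of blood draw, breath test and questionnaire within the evening is not set, so samples may precede any cue. Cigarettes are dispensed singly with times logged from Day -1 (Protocol 6.5.1), so a late change in smoking would be visible.

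A reader might draw three stronger conclusions that the documents do not support.
- *All subjects learn their arm.* Recipients learn only that they are not in SA.
- *The primary comparison is compromised.* THS 2.2 and CC subjects receive the same cue. The remaining route is indirect: SAP 12.6 puts all three arms in every model, so SA baselines contribute to the common covariate slope.
- *Staff should not use the allocation on Day 0.* The study is open-label and investigators know the arm (Protocol 6.4, SAP 6.3.2); only subjects are to remain uninformed.

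SAP 6.3.2 also describes subjects as unblinded after randomization. That does not remove the conflict, because SAP 6.1 still places disclosure on Day 1.

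**Conclusion.** The inconsistency is real and sits within one table. As written, the Day 0 schedule either gives SA subjects (40 of 160) a cue to their allocation 7.5 to 10.5 hours before 06:30 AM on Day 1, or cannot be carried out.

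An effect on the data requires that randomization precede the form, that SA subjects recognise the omission, and that they then change their smoking or ratings before the baseline value is complete. The documents do not show how often this would happen, so the size is unknown. The comparisons mainly exposed are THS 2.2 versus SA, which are secondary and exploratory; the QSU-brief baseline, a self-rating collected in the same window, is the most exposed. Little direct bias is expected in the primary THS 2.2 versus CC comparison. The case for acting is that the Protocol's own concealment step can be preserved at almost no cost.

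**What to change.** Give the MCEQ to all subjects on Day -1 and Day 0, and apply the arm restriction only from Day 1, as footnote m already does for HST.

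Changing Table 9 alone would leave it contradicting other sections. Align these together:
- Protocol Section 7.8.4.3, Table 9, and the MCEQ row and footnote l of Table A1;
- SAP Sections 7.3.3 and 12.6.3.1.2, and SAP Table A1.

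The SA baseline forms need not be analysed; the MCEQ comparison stays THS 2.2 versus CC. The cost is one 12-item form for about 40 more subjects on one evening, since Table 8 already gives the form to everyone on Day -1, plus the wording changes.
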